Sub study: From an economic perspective, anxiety confers a high economic burden on the individual, state and national level. Based on data from 2002, the annual cost of anxiety disorders in the United States is likely to be more than \$100 billion. These cost estimates are 16 years old and an updated examination of the cost of pediatric anxiety disorders is needed. Research has not investigated the potential financial benefit (e.g. school attendance, standardized test scores) or fiscal feasibility of adopting these interventions relative to current practices. Within the United States, it is also uncertain whether the cost burden of pediatric anxiety varies by demographic factors (e.g. minority status, socio-economic status, gender). Each of these cost factors represent sizable gaps in scientific knowledge. In this context, a Pre-K award was submitted to the Connecticut Institute for Clinical and Translational Science in order to fill this important gap in the scientific literature. This sub study will examine the cost of pediatric anxiety and the relative benefit of TAPES compared to usual care (UC). The purpose of this costs and benefits analysis is to provide information to school system administrators and teachers regarding the budgetary consequences of pediatric anxiety and to summarize the cost of achieving potential improvements in school functioning.

Procedures for Summer Months. We will only randomize teachers and enroll students if at least 10 weeks of school remain in the academic year to allow sufficient time to complete baseline evaluation, TAPES implementation and post evaluations.

Randomization. During the RCT, randomization will occur at the teacher level at a 1:1 (20 TAPES: 20 TAT). The randomization plan will be generated prior to the identification of teachers to minimize potential biases. Randomizing teachers to two active training conditions was selected for several reasons. The current design allows for all teachers to receive some training in anxiety identification and reduction—a major recruitment barrier in our previous school-based trials where clinicians or nurses were assigned to a no training control condition and subsequently dropped from the study. In addition, this design allows for an examination of a brief teacher training which represents typical teacher professional development offerings in CT.

Participants and Recruitment

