Aim #1: To develop and assess the usability, acceptability and feasibility of TAPES, a teacher training to reduce student anxiety. To address this aim, quantitative and qualitative data collected from the DT's initial review of materials and participants' (teachers, children and parents) data in the open trials will be recorded and synthesized in a descriptive manner. The PIs and DT will use this information to refine TAPES' training materials. Additional information regarding feasibility and acceptability will be collected throughout the study (e.g., obtaining reasons for declining initial participation and reasons for drop outs, and evaluating satisfaction). We will review mean scores on measures of satisfaction (e.g., Training Satisfaction and Feedback Questionnaire, TAPES Satisfaction and Feedback Questionnaire) as well as participants' responses to open ended questions on these measures. Moreover comments from the teacher Exit Interviews will enable us to modify individual components in TAPES to enhance its usability, acceptability and feasibility for Stage three. During the pilot RCT in Stage three, ANCOVA will be used to compare TAPES with TAT in terms of usability, acceptability, and feasibility based on the same satisfaction measures. If needed, we will use teacher-specific (e.g., years of teaching experience, teaching efficacy) and child-specific (e.g., age, baseline anxiety severity) as covariates. For example teachers' rating on intervention acceptability will be modeled as y_{ij} = $\mu + \tau_i + B(x_{ij} - \bar{x}_i) + \varepsilon_{ij}$ where *i* indicates teacher-level randomized intervention-training group assignment, say 1 for TAPES, and 0 for TAT, y_{ij} denotes the rating from the jth teacher in group *i* at post training, x_{ij} denotes teacher-specific covariates, and ε_{ij} denotes the unobserved error term. If the null hypothesis $\tau_0 = \tau_1$ is rejected, it implies that teacher's view on

acceptability depends on their assigned group. In addition, weekly data from *Teacher and Child Recruitment Tracker*, *Teacher Time Log*, and *Teacher and Child Retention Tracker* will be used to assess feasibility.

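### The example Aim 1 ANCOVA centres its covariate at each arm's own mean; coded as printed, it leaves the arm difference unadjusted but uses a covariate-reduced standard error, so the test can exceed its nominal level

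*Combined protocol and SAP*

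**What the plan says.** The Data Analytic Plan, under Aim #1, proposes ANCOVA to compare TAPES with TAT on usability, acceptability and feasibility in the pilot RCT. Covariates are conditional: "If needed, we will use teacher-specific (e.g., years of teaching experience, teaching efficacy) and child-specific (e.g., age, baseline anxiety severity) as covariates".

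The plan then gives a worked example for teachers' acceptability ratings, whose right-hand side is μ plus "\tau_i + B(x_{ij} - \bar{x}_i) + \varepsilon_{ij". Its terms are defined there:

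- The first index, i, is the arm: it "indicates teacher-level randomized intervention-training group assignment, say 1 for TAPES, and 0 for TAT".
- The outcome is a single score for each teacher j: it "denotes the rating from the jth teacher in group *i* at post training".
- The covariate term, x with both indices, stands for characteristics of the teacher.

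The hypothesis tested is τ₀ = τ₁. This is the only model equation given for Aim 1. Under Randomization, the plan states that "randomization will occur at the teacher level at a 1:1 (20 TAPES: 20 TAT".

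**The concern.** By the plan's own definitions, x̄ with the single subscript i is the mean of the covariate among teachers in arm i. An ordinary ANCOVA uses one common centre for both arms, or none. The difference is more than cosmetic. Centring at a common value changes only the intercept, whereas centring at each arm's own mean removes the between-arm part of the covariate and so changes the arm contrast.

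At stake is the validity of the Aim 1 test and its confidence interval. A chance difference between arms in, say, teaching efficacy would stay in the estimate, while the standard error would be that of an adjusted estimate that was never computed. The better the covariate predicts the rating, the larger the mismatch.

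**Working it through.** **Inputs**

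- Model and index definitions: Data Analytic Plan, Aim #1.
- n = 20 teachers per arm: Randomization.
- Level 0.05: stated only in the Power Analysis, for teacher knowledge and child anxiety. Its use for Aim 1, and two-sidedness, are assumptions.
- Within-arm covariate-outcome correlation ρ: not in the documents, so varied from 0 to 0.8.

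The plan states no error rate for this analysis, so there is no figure of its own to reproduce.

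**Step 1: what the printed model estimates.** Within each arm the deviations x_ij − x̄_i sum to zero, so the centred covariate is orthogonal to the arm indicator. Hence

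- printed model: estimate of τ₁ − τ₀ = ȳ₁ − ȳ₀
- ordinary ANCOVA: estimate of τ₁ − τ₀ = (ȳ₁ − ȳ₀) − B̂(x̄₁ − x̄₀)

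Both have the same B̂ and the same residual sum of squares. Only the second removes the covariate imbalance.

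**Step 2: true and reported variance.** Let σ² be the within-arm variance of the rating.

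- True variance of ȳ₁ − ȳ₀ over repeated randomisation: 2σ²/n
- Variance the printed model reports (large sample): 2σ²(1 − ρ²)/n

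With n = 20, the true SE is √(2/20) = 0.316 SD at every ρ. At ρ = 0.7 the reported SE is 0.316 × √(1 − 0.49) = 0.226 SD.

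**Step 3: size of the test.** Type I error = 2[1 − Φ(1.96 √(1 − ρ²))]. For example, at ρ = 0.5 the effective critical value is 1.96 × √0.75 = 1.70, which gives 9.0%.

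**Step 4: check by simulation.** The settings were 20 vs 20 teachers, no true effect, one covariate, 100,000 trials per ρ, and a t test on 40 − 2 − 1 = 37 degrees of freedom.

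| ρ (assumed) | Printed model, formula | Printed model, simulated | Overall-mean centring, simulated |
|---|---|---|---|
| 0 | 5.0% | 5.0% | 5.0% |
| 0.2 | 5.5% | 5.4% | 5.1% |
| 0.3 | 6.2% | 6.1% | 5.1% |
| 0.5 | 9.0% | 8.7% | 5.0% |
| 0.6 | 11.7% | 11.4% | 5.1% |
| 0.7 | 16.2% | 15.7% | 5.0% |
| 0.8 | 24.0% | 23.1% | 4.9% |

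Two covariates, only one of them predictive, give nearly the same values. The printed model's estimate keeps a correlation of about ρ with the chance covariate imbalance. With overall-mean centring that correlation is about 0.

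By the same formula, a nominal 95% interval would cover about 100 − 9.0 = 91.0% of the time at ρ = 0.5 and 100 − 16.2 = 83.8% at ρ = 0.7.

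**The case against.** **It may be a notation slip.** The case rests on one subscript under an overbar, in text read from a PDF by a program. The plan calls the method ANCOVA, nowhere says in prose that covariates will be centred within arm, and enters the pre-training score uncentred in the Aim #3 knowledge model. An analyst who fits standard ANCOVA software with the raw covariate gets a valid 5% test. This stands: the text cannot settle whether the subscript was intended. But a lost dot after the i would still leave the arm mean, and a grand mean would carry no i. If it is a slip, the equation still contradicts the method named beside it and should be corrected.

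**The model is conditional and illustrative.** Covariates enter only where judged necessary, and the equation is offered as an example. Without a covariate, the comparison is a valid two-group test. This also stands and limits the reach of the point. It does not remove it, because the plan does not say when covariates would be needed, and this is the form an analyst would copy.

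**Some measures may not allow adjustment.** The Training Satisfaction and Feedback Questionnaire, which Table 1 schedules after training, is described under Feasibility Measures as anonymous. Unless responses can be linked to teachers, teacher covariates cannot be fitted to it. This is correct for that instrument. The TAPES and TAT satisfaction questionnaires are not described as anonymous.

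**Nothing supports a strong correlation.** The named covariates are years of experience and teaching efficacy, and the outcome is a rating of acceptability. The section on the theory of teacher behavior change says self-efficacy influences adoption and use of new skills, so a zero correlation cannot be presumed. No value follows from that.

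**Conclusion.** The point holds as a conditional one. If a covariate is included and the printed equation is coded literally, the Aim 1 test of τ₀ = τ₁ compares an unadjusted difference with a standard error that is too small. Under the assumptions above, type I error runs from about 5% (ρ of 0 to 0.2) through 6% (0.3) and 9% (0.5) to 16% (0.7).

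Three stronger readings are tempting, and the documents do not support them.

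- A reader might infer a false-positive rate of 9 to 16%. That needs ρ between 0.5 and 0.7, which the plan does not supply; at 0.3 or below the excess is about one percentage point or less.
- A reader might infer that the primary analysis is affected. It is not shown to be: the primary outcomes belong to Aim #3, and its knowledge model does not centre within arm.
- A reader might infer that the plan adds covariates to correct imbalance and fails in that purpose. The Aim #1 text gives no purpose for the covariates.

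Severity is minor to moderate. Aim 1 also relies heavily on descriptive and qualitative material, and no progression decision is tied to this p-value. The equation is nevertheless wrong as written.

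**What to change.** Replace the arm mean with the overall covariate mean across both arms:

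y_ij = μ + τ_i + B(x_ij − x̄) + ε_ij

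where x̄ is taken over all randomised teachers in the analysis. Entering x_ij uncentred with an arm indicator gives the same arm contrast and the same test. Use this form in every covariate-adjusted Aim 1 comparison. State the significance level and sidedness for Aim 1 in the same place, since neither is given there.

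The cost is one symbol and a sentence of text. No change to data collection, sample size or conduct is needed.

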Summary, Benefit to Stakeholders, and Aims: Teachers lack the knowledge and skills to support the learning of students with excessive anxiety who have, or at risk of developing, an IDEA disability. Excessive student anxiety is a common problem that severely impairs short and long term academic functioning and increases teacher burden. Conversely, reducing student anxiety has been associated with improvement in educational functioning. Because anxiety manifests daily in the classroom, teachers are in an ideal position to identify and help students manage their anxiety. One universal intervention for anxiety reduction exists, but its feasibility and efficacy are not established. The aims of this application are to address this gap in teacher training. Specifically, the aims of this proposal include: Aim 1) to develop the *Teacher Anxiety* Program for Elementary Students (TAPES) and assess its usability, acceptability and feasibility; Aim 2) to determine whether teachers can implement TAPES with high fidelity and quality; Aim 3) to examine the impact of TAPES, compared to a standard professional development condition, on teacher a) knowledge and b) use of anxiety reduction strategies with students with excessive anxiety (Primary Outcomes); and Aim 4) to examine the impact of TAPES on student outcomes. Exploratory aims will examine the mediators (proposed in the theory of change, see Figure 1 in Appendix) and predictors and moderators of TAPES impact on teachers knowledge and skill. If effective, TAPES has the potential to directly benefit: 1) teachers--by providing training in an important and relevant, but neglected area that will enhance their professional development and effectiveness in the classroom; and 2) children--by reducing their anxiety and improving their educational, social, and behavioral functioning. This development process will be led by a research team with over two decades of experience developing and evaluating feasible and effective trainings and interventions for school personnel ([name] et al., 2012, 2016). It will also be supported by a Development Team (DT) comprised of national teacher training experts, teachers, and CT State Board of Education representatives.

Preliminary study: Survey of current teacher practices for anxious youth. In preparation for the current application, we undertook a survey with 13 CT elementary teachers and school

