Overview: Design and Methods. This three-year development project consists of 3 stages. **Stage one** (months 1-6) involves establishing a Development Team (DT) that will review the initial draft of TAPES and provide feedback to ensure that TAPES is acceptable to teachers and feasible for the school setting. **Stage two** (months 7-20) involves two successive open trials of the TAPES protocol with 15 teachers and 20 children. This stage will allow for "trial runs" of the training to assess feasibility, acceptability and utility of the training. Data and qualitative feedback gleaned during the first open trial will inform modifications for the second open trial. We will present and discuss data with the DT after each open trial. We will also ask 5 teachers from open trial 1 to test out the revisions for open trial 2. Based on knowledge gained in this stage, appropriate modifications will be made for stage three. **Stage three** (months 21-34) involves a pilot RCT using a randomized controlled design comparing TAPES to the Teacher Anxiety Training (TAT). TAT (developed by the PIs for use in other studies and described below) will be used to represent "typical" teacher professional development training. The RCT will be conducted in three phases. Phase 1 consists of recruiting, randomizing, and training

teachers in either TAPES or TAT. Also during this phase (but after the training), teachers will recruit anxious children and study staff will screen and evaluate them to determine eligibility. In Phase 2 teachers will implement TAPES or TAT. Phase 3 involves a post-intervention (after 8 weeks) and a three-month follow-up assessment of the primary (teacher behavior) and secondary (child) outcomes. Trained independent evaluators (IEs) will assess primary outcomes (teacher behavior). The culmination of these iterative stages will be a final version of the training that will be ready for evaluation in a larger efficacy trial.

DETAILED DESCRIPTION OF EACH STAGE

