TAT: TAT is a 3-hour didactic training on student anxiety that the PIs use in their ongoing school-based studies for school clinicians and nurses (modified for teachers). The TAT content will include information on the signs, causes, consequences, and effective interventions for student anxiety. As noted earlier, this control condition was selected to enhance teacher recruitment and mimic the format of teacher professional development trainings in CT. Thus, TAT will provide a credible and acceptable control. An added value of this proposal will be to examine the impact of TAT on teacher behavior and child outcomes relative to TAPES. Independent Evaluator (IE) Training. IEs will have a masters or doctoral degree in a relevant child mental health field and experience with conducting diagnostic assessments with anxious youth. Training and certification of IEs will include completion of: 1) didactic training that includes review and practice of all assessment measures and study procedures by the PIs, 2) review of ADIS videotaped administrations by a senior interviewer, 3) achieving inter-rater reliability (kappa) of .85 for the severity ratings on 3 cases (live or with videotapes) and 4) administration of the ADIS in the presence of a senior interviewer. All assessments will be videotaped and a random 15% of tapes will be evaluated for interrater reliability (i.e., for the severity ratings).

Measures. The selection of proposed measures to be used in Stages 2 and 3 was guided by the best available measures for the study aims and proposed theory of change, and participant burden. Measures, informants, and time points are listed in Table 1. Data will be collected from multiple informants (e.g., teacher, IEs, parent, child) using multiple formats (e.g., classroom observations, rating scales, interviews, school records). *Many of the measures were used in the*

PI's previous school-based intervention development studies and will be modified for TAPES. The assessment battery will also be modified based on DT and open trial feedback. Measures to be developed and used in the sub-study are also included in this section.

Primary Outcomes: Teacher Knowledge and Skills

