Aim #2: To determine whether teachers can implement the TAPES skills with fidelity/quality. Descriptive statistics will be used to test this aim. We will examine mean scores over time on our fidelity measures (e.g., *S-H Meeting Fidelity and Quality Measure*) to determine the ability of teachers to implement TAPES skills accurately and with high quality. We will also examine which teacher-specific and child-specific variables affect fidelity ratings.

Aim #3 (Primary Outcome): To assess the impact of TAPES, compared to TAT, on teachers' a) *knowledge* regarding student anxiety symptoms and anxiety reduction strategies and b) use of anxiety reduction skills in classroom. To achieve this aim, we will first assess the equivalence of teachers randomized into either TAPES or TAT on baseline teacher (years of experience,

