burnout, teacher efficacy; teacher behavior) and child characteristics (e.g., gender, age, baseline anxiety symptoms, classroom functioning). To test the main hypothesis, that teachers in TAPES, compared to TAT, will have higher knowledge about anxiety reduction, we will examine scores on the *Teacher Knowledge Assessment* at post-training, and at the end of school year as outcomes in GLM controlling for teacher pre-training score. Let y_i denote the post-training or end of school year test score of teacher i, x_{i1} and x_{i2} denote teacher i's group assignment and pre-training test score, respectively, and ε_i denote resident term. Rejecting $\beta_1 \leq 0$ and $\beta_3 \leq 0$ in the model: $y_i = \beta_0 + \beta_1 \times x_{i1} + \beta_2 \times x_{i2} + \beta_3 \times x_{i1} \times x_{i2} + \varepsilon_i$ suggests that TAPES teachers' post-training test scores are higher and they have a greater gain in knowledge than TAT teachers. Teacher-specific covariates can be added to the above model as needed. To test the hypothesis that TAPES, compared to TAT, will result in greater use of anxiety reduction skills in the classroom, IE's Classroom Observation of Teachers Skills rating for each pair of teacher and anxious student at baseline, post-intervention, and 3-month follow-up will be modeled in GLMM. Now rating, y_{ijk} are nested within teacher k and student j, who is nested within teacher k, in the multilevel equations: Level 1: $y_{ijk} = \pi_{0jk} + \pi_{1jk} \times \text{timepoint}_{ijk} + e_{ijk}$; Level 2: $\pi_{0jk} = \beta_{00k} + r_{0jk}$ and $\pi_{1jk} = \beta_{10k} + r_{1jk}$; Level 3: $\beta_{00k} = \gamma_{000} + \gamma_{001} \times w_k + u_{00k}$ and $\beta_{10k} = \gamma_{100} + \gamma_{101} \times w_k + u_{10k}$; where w_k denotes teacher k's intervention-training group assignment with e, r, and u representing error terms in the respective levels. Teacher-specific (e.g., years of teaching experience, teaching efficacy) and child-specific (e.g., age, baseline anxiety severity) covariates can be added to Levels 2 and 3 equations as needed. Aim #4 (Secondary Outcomes): To examine the impact of TAPES relative to TAT on student outcomes. Change scores on student mental health (e.g., Spence Children's Anxiety Scale, SCAS) and academic achievement (e.g., Woodcock-Johnson Tests of Achievement) from pre-to postintervention and 3-month follow-up will be modeled as GLMM similar to above in Aim 3. **Exploratory aims**: To examine mediators (proposed in the theory of change, see Figure 1 in Appendix) and predictors and moderators (e.g. Teacher Background Form, MBI-Educators Scale) of TAPES impact on teacher knowledge and behavior. Structural equation modeling (SEM) will be used to explore potential predictors (e.g., baseline teacher burnout as measured by MBI-ES), mediators (e.g., subscale scores from the OSTES) and moderators (e.g., years of teacher experience) on teacher behavior change (e.g., change score on the Classroom Observation of Teachers Skills at pre-, post-intervention and 3-month follow-up). Sub study: Aim #1: Assess the direct and indirect cost of pediatric anxiety among youth enrolled in the TAPES intervention. This aim involves the modification of existing measures of direct and indirect cost. These measures will be administered to parents and teachers at existing TAPES assessment time points (i.e. baseline, post intervention and three-month follow up). Aim #1a: Estimating the cost of pediatric anxiety through direct and indirect costs. Aim #2: To examine the child and parent benefit of TAPES compared to UC. This aim involves estimating the cost of TAPES relative to the UC condition in relation to direct and indirect costs. Exploratory Aim: To examine family demographic factors as moderators of pediatric anxiety cost. **Power Analysis.** Although this is a development study proposing a small pilot RCT, attempts were made to estimate statistical power for the key outcomes based on existing literatures on similar measures (see White et al., 2011 for Teacher Knowledge Assessment and Barrett et al., 2005 for child anxiety using the SCAS). Using Optimal Design version 3.0 calculations for both variables were based on an anticipated enrollment of 20 teachers in each group (and 1-2 students per teacher). We assumed a conservative within-teacher ICC of 0.10 (Eldridge et al., 2004) and

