
an alpha level was set at .05. Below is a list of minimum effect sizes (calculated as within-group difference in change score, divided by the pooled standard deviation) needed to be detectable with 80% power. With 20 teachers in each group, we will have 80% power to detect the effect size found by White et al. (2011) of d = 1.19 on teacher knowledge. With 30 students in each group, we will have 80% power to detect the effect size found by Barret et al. (2005) of d = .92on child anxiety (effect sizes based on moderately anxious students at pre-post timepoints). Time Table : We are requesting funds for three years. The first six months will be for administrative study start-up tasks (hiring, IRB approval), IE training, and TAPES refinement and review of materials with DT (Stage 1). Months 7 - 20 (Stage 2) will be devoted to recruitment of teachers and students for open trials and further adaptation and refinement of TAPES. Months 21 to 34 will be devoted to implementing the RCT. The final two months (35-36) will be devoted to completing data analyses and manuscript preparation. Personnel: Relevant Expertise of Research Team. The core UCHC research team (Drs. [name] & [name]) along with our consultants have over 20 years of experience in conducting research on the development, evaluation, and dissemination of school-based programs for teachers and school personnel. In addition, the team has extensive experience providing education and training in anxiety reduction skills to school-based and community personnel. Both [name] & [name] moved to UCHC in 2014. In that time they have successfully partnered with 7 CT school districts which now serve as authentic environments for their funded research. They have trained over 40 school clinicians and 17 school nurses as part of their research-exceeding initial recruitment goals. Together they also established the Child/Adolescent Anxiety and Mood Program (CAMP). CAMP conducts community-based research focusing on child and adolescent anxiety and mood disorders, with an emphasis on intervention and dissemination. CAMP now has research coordinators, postdoctoral fellows, and research assistants who work together to recruit research participants and implement studies funded by NIMH and IES. CAMP holds weekly and monthly research meetings that are attended by residents, fellows, and faculty. Currently, CAMP members include 2 faculty, 3 postdocs, 2 Masters level staff, and 8 student research assistants. Finally, Drs. [name] and [name] share responsibility for teaching seminars on child anxiety for psychiatry residents at UCHC. Together, they have given numerous seminars and presentations on childhood anxiety and CBT to a variety of audiences (e.g., parents, teachers, counselors, physicians, and psychiatrists) and have trained school-based clinicians and nurses in the principles and strategies of delivering CBT to anxious youth within schools. These prior experiences have prepared the investigative team to successfully conduct this proposed study. This project reflects a significant and logical next step in this program of research by training teachers in the identification and support of anxious youth. Below is a list of key personnel that will also support this grant, their qualifications, roles, responsibilities, and percent of time and calendar months per year to be devoted to the project are listed below. Evidence of publishing in peer-reviewed scientific journals is documented in the biosketches. Each team member has experience that will ensure the successful implementation of this study.

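### The plan describes its primary outcome inconsistently and gives its primary tests neither multiplicity control nor a rule for success

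*Combined protocol and SAP*

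**What the plan says.** **Both outcomes primary.** The Summary, Benefit to Stakeholders, and Aims section lists knowledge and "use of anxiety reduction strategies with students with excessive anxiety (Primary Outcomes". The Measures section has the heading "Primary Outcomes: Teacher Knowledge and Skills", and Table 1 repeats it. The analysis plan opens with "Aim #3 (Primary Outcome): To assess the impact of TAPES, compared to TAT, on teachers" and then lists knowledge and skill use as parts a and b.

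**Behavior only.** The Overview: Design and Methods refers to a "three-month follow-up assessment of the primary (teacher behavior) and secondary (child) outcomes". The Child Inclusion/Exclusion Criteria likewise give change in teacher behavior as the primary aim.

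**Knowledge foremost.** Aim #3 begins its tests with "To test the main hypothesis, that teachers in TAPES, compared to TAT, will have higher knowledge about anxiety reduction".

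**The tests.** Knowledge scores are examined "at post-training, and at the end of school year as outcomes in GLM", adjusted for the pre-training score. The model contains a group term (β1) and a group-by-pre-score term (β3), and the stated rule is to reject one-sided nulls on both. Skills are analysed in one three-level GLMM over baseline, post-intervention and 3-month follow-up, with a group effect on the slope (γ101).

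**Error rate.** The Power Analysis says "an alpha level was set at .05" and does not state sidedness. It covers knowledge and child anxiety, not classroom skills.

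**The concern.** A reader of the results needs to know in advance which finding makes the trial positive on its primary outcome. The plan offers two primaries, puts knowledge first in one place and omits it in another, and gives no rule for combining the tests. Two consequences follow.

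- With several tests and no stated control, the chance of at least one false primary rejection can exceed the single alpha in the document.
- Nothing prevents a positive knowledge test from being reported as meeting the primary outcome while classroom behavior is unchanged. Knowledge is the easier target: TAPES provides about 8 hours of training plus weekly consultation and classroom coaching, against a 3-hour didactic session for TAT. It is also the only primary with a power figure.

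The RCT is meant to produce a training ready for a larger efficacy trial, so what counts as success affects the next decision.

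**Working it through.** **1. The plan's own figure.** Inputs from the Power Analysis are 20 teachers per group, d = 1.19, alpha .05 and stated power 80%. Knowledge has one score per teacher, so the ICC does not enter.
- Noncentrality: d√(n/2) = 1.19 × √10 = 3.763.
- Normal approximation, two-sided: Φ(3.763 − 1.960) = Φ(1.803) = 96.4%. Noncentral t with 38 df: 95.6%. One-sided, t: 98.0%.
- Effect detectable with 80% power, two-sided: (1.960 + 0.842) × √(2/20) = 0.89 by the normal approximation and 0.91 by t.

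The stated 80% is therefore true only as at least 80%. The difference is conservative and does not bear on this point, but it leaves room for a stricter alpha.

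**2. Counting the tests.** Knowledge at two times plus one longitudinal skills model makes three tests, provided that each knowledge model contributes one.

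**3. Error rate if each test is run at .05.** The .05 per test is an assumption.
- Two independent tests (knowledge once, skills once): 1 − .95² = 9.75%.
- Three independent tests: 1 − .95³ = 14.3%.
- Upper bound for three: 3 × .05 = 15%.
- Three correlated tests (simulation, 2,000,000 draws). The documents give no correlations, so a range was assumed:

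| Correlation, knowledge–knowledge | Correlation, knowledge–skills | Two-sided | One-sided |
|---|---|---|---|
| 0.5 | 0 | 13.6% | 13.3% |
| 0.7 | 0.3 | 12.6% | 12.0% |
| 0.9 | 0.5 | 10.8% | 10.3% |

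The range is about 10% to 14%.

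**4. Effect of the β1 and β3 rule.** The rule was simulated under the null with 20 teachers per arm, one-sided .05, an assumed pre–post correlation of .5, and 20,000 runs.
- *Both must be rejected.* With the pre-score centred, this happens in 0.265% of runs per time point. Treating the tests as independent, the total is 1 − (1 − .00265)² × .95 = 5.5%. With an uncentred pre-score whose mean lies 3 SD above zero, both were never rejected, so the total is 5.0%.
- *Either counts.* There are then five tests: 1 − .95⁵ = 22.6%.

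**5. Two primaries, one test each.** At two-sided .025, the stricter Holm step, knowledge power at d = 1.19 is Φ(3.763 − 2.241) = 93.6% by the normal approximation and 91.9% by t. The detectable effect is 1.01 SD. No such calculation is possible for skills, because the documents give no effect size.

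**The case against.** **The naming conflict may be loose wording.** The aims, the Measures heading, the Table 1 heading and Aim #3 all agree on knowledge plus skills. The parenthesis in the design overview and the sentence in the child criteria mainly contrast teacher with child outcomes, and the knowledge sentence introduces part a of a two-part aim. This is fair, and it shows which definition should prevail. The conflicting sentences are still current text, and they differ on whether knowledge is primary at all and whether it comes first.

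**The inflation is not fixed by the text.** This stands. No alpha is assigned to the Aim #3 tests, so .05 each is inferred from the power section. A reader might go further and count skills separately at post-intervention and at 3 months. Four independent tests would give 1 − .95⁴ = 18.5%. The documents do not support that count, because skills enter one model with one group-by-time coefficient.

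**A false rejection is not always a false success for TAPES.** Correct if tests are two-sided, since half of false rejections favour TAT. The chance of a false result in favour of TAPES is then 1 − .975³ = 7.3% for three independent tests and 1 − .975² = 4.9% for two. The knowledge rule is written with one-sided nulls, however, and at one-sided .05 every false rejection favours TAPES.

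**This is a pilot.** The plan calls the trial a small pilot within a development study, and strict family-wise control there is partly a matter of preference. That lowers the stakes. But the plan states directional hypotheses, rejection rules, an alpha and a power, so it needs one consistent primary definition and a decision rule.

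**Conclusion.** The concern holds. The primary outcome is described inconsistently in current text, and the primary tests have no multiplicity control or success rule. That conclusion needs no assumption.

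The size of the error inflation does rest on assumptions. If three tests are each run at .05, the chance of at least one false primary rejection is about 10% to 14%, and 15% at most; for two independent tests it is 9.75%. Under other readings of the β1 and β3 rule the figure runs from about 5.5% to about 23%. The plan therefore does not determine its own error rate, and no single value should be quoted as the plan's.

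A reader might infer that the investigators intend to claim success on knowledge alone. The documents do not say so. They only lack a rule that would prevent it.

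**What to change.** 1. Keep both primaries, with one confirmatory test each: the group effect on knowledge at post-training, and the group-by-time coefficient for skills (γ101) from the GLMM already specified. Skills then keep the planned model and contrast.
2. Define the knowledge effect at the mean pre-training score, by centring that score. With an uncentred score and the interaction in the model, β1 is the group difference at a pre-score of zero.
3. Reconcile the knowledge time point with Table 1. It lists the test only at BL and PO, uses a separate post-training label for another instrument, and has no end-of-year label.
4. Test the two primaries with Holm at family-wise .05 and state the sidedness. Label end-of-year knowledge, β3 and all other contrasts secondary.
5. State that each outcome is reported by name and that a knowledge result alone does not support a claim of changed teacher behavior. Holm by itself would still allow knowledge to succeed as a primary while skills do not, so this sentence is needed as well.
6. Align the design overview, the child criteria and the text of Aim #3 with the aims, the Measures heading and the Aim #3 heading.

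**Cost.** No new data and no change in sample size. If testing is two-sided, the detectable knowledge effect at the stricter Holm step rises from 0.91 to 1.01 SD, and power at d = 1.19 falls from 95.6% to 91.9%. If testing is one-sided, the corresponding changes are 0.80 to 0.91 SD and 98.0% to 95.6%. Skills also lose some power at the stricter step, but the amount cannot be computed from the documents. End-of-year knowledge loses its standing as a primary result.
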